***PI must attest that all of the following are true.***

*\* The risk is justified by the anticipated benefit to the subjects.*

*\* The relation of the anticipated benefit to the risk is at least as favorable to the subjects as that presented by available alternative approaches.*

*\* The proposed plan for the assessment of the capacity to consent is adequate (and the PI states he/she will comply with institutional policy GPP-312).*

*\* The assessment of the capacity to consent will be performed by a qualified attending physician with appropriate training, licensing and certification, with special attention paid to qualifications re: assessing incapacity due to mental illness, mental retardation or developmental disability.*

*\* The proposed plan for the assessment of capacity includes the assessment of the cause and extent of the incapacity and likelihood that the subject will regain capacity.*

*\* The PI has indicated that he/she will document this determination with the above details of the assessment appropriately (eg. In the medical record when applicable and in research record).*

*\* The consent document includes a signature line for a legally authorized representative.*

## **12. Procedures - Narrative**

### **Description of the Study Design**

The study is a randomized controlled trial design. Participating dyads will be randomized to receive either the intervention (home based palliative care) or usual care, in a 1:1 randomization, parallel design.

The patient/ caregiver dyad will not be blinded. However, the research coordinator (outcome assessor) conducting the follow-up interviews will be unaware of assignment, hence calling this a single-blind trial.

### **Description of Procedures Being Performed**

#### **Intervention dyads**

For intervention dyads, the CHW, RN, and SW team conduct in-depth intake assessments that may include assessment of the following: disease stage (RN); physical, psychological and behavioral symptoms (RN); cognitive, functional and nutritional status (RN); medication reconciliation (RN); durable medical equipment needs (RN); dyad understanding of disease, goals of care, and advance directives (RN+SW); caregiver support network (SW); caregiver burden and unmet needs (SW); legal, financial and insurance needs (SW); spiritual concerns (SW). The CHWs accompany the RN and SW on initial visits to develop an understanding of the family and cultural context and their need for connections to community resources. The care team creates a comprehensive care plan to address the needs identified at the intake assessment. The care plan is implemented with the support of the CHWs, SW and RN and evaluated regularly. From 3/19/20 and due to the COVID-19 pandemic, all initial video visits and subsequent assessments will be conducted using video visit software. However, in the exceptional case that the patient has a clinical emergency that, according to the MD/NP cannot be managed using telemedicine and/or transfer to the hospital (e.g., uncontrolled agitation in a patient whose goals of care are to remain at home) we will consider the option of a home visit, after a thorough assessment and documentation in the clinical record of the risks and benefits, and guided by Institutional procedures for home visits in the context of the COVID-19 emergency which include strict adherence to infection control procedures. Note, to provide for this unlikely event, all team members have been trained in the use of personal protective equipment.

As a co-management model, the team works collaboratively with the PCP and existing in-home services such as home health aides or visiting nurse services with the goal to provide an added layer of support, rather than replace existing care.

Frequency of contacts with the team will be individualized according to the dyad's needs. Some assessments will include multiple team members simultaneously while others will be done individually. Intervention dyads receive access to 24-hour telemedicine support, using the pre-existing infrastructure within our Department. We will also use Mount Sinai's 24/7 community paramedic program whereby physicians can dispatch Mount Sinai paramedics to provide in-home treatments without automatic transport to the emergency department. Community paramedicine are operating under guidelines to reduce the risk of COVID-19 transmission.

At the end of their time on the program, the dyad continues care with their usual providers, or is referred onward to other services as appropriate (e.g., Mount Sinai Visiting Doctors, hospice).

#### **Control dyads**

Dyads randomized to control will continue to receive care with their usual care providers. In addition, a copy of their baseline assessment will be uploaded into the EMR with the subject's consent, and the provider notified of this by email, with explicit notification of any areas for concern (i.e., uncontrolled symptoms). In addition, the caregiver-subject within control dyads will receive a health coach who will identify a physical health goal with the caregiver (e.g. weight reduction, smoking cessation) and work, through monthly visits, towards this goal. This control arm will assure balance between the groups in terms of "attention received" in a way that will not impact study outcomes.

#### **All dyads - data collection**

For dyads in both arms, there will be an interview undertaken at baseline, 3 months, and 6 months. This will be undertaken either in person (at the dyad's home or a Mount Sinai facility) or over the telephone. At all times confidentiality will be assured. These interviews will last around 30 minutes.

Any concerns that arise during interview will be shared with the patient's treating provider (either the palliative care team or for control patients, their PCP).

### **Description of the Source Records that Will Be Used to Collect Data About Subjects**

1. EMR - we will abstract data from the patient's EMR at baseline, 3 months, and 6 months and after every hospitalization.
2. Mount Sinai Data Warehouse. We will request data on utilization and costs of care from the data warehouse on enrolled subjects.
3. Claims databases. We will request claims data for enrolled patients (using the same variables as the data warehouse) to study the impact of the intervention on utilization and costs.

**Description of Data that Will Be Collected Including Long-Term Follow-Up**

1. Patient/ proxy and caregiver reported data - through interviews.

Data to be collected will include: (i) patient demographics; (ii) symptoms; (iii) quality of life; (iv) resource use; (v) physical function; (vi) agitation; (vii) care preferences; (viii) financial burden.

We will obtain information from the patient's caregiver (as a subject) about: (i) caregiver demographics; (ii) caregiver health; (iii) caregiver function; (iv) caregiver burden; (v) caregiver depression; (vi) caregiver satisfaction; (vii) caregiver self-efficacy.

2. Data warehouse/ claims database (ClaimsStar)

We will abstract data from the data warehouse and the claims database on utilization, diagnoses, and costs of care.

**Research Requires HIV Testing**      No

**13. Procedures - Genetic Testing**

Genetic Testing Will Be Performed  No

***Guidance and Policies > Future Use Data Sharing and Genetic Research***

**14. Procedures - Details****Surveys or Interviews**

Yes

**Type of Instruments Being Used**

Standardized, Created By Research Team

**Names of Standardized Instruments**

1. Symptom management at the end of life in dementia
2. Quality of Life in Alzheimers Disease
3. Zarit Burden Inventory (caregiver subject)
4. Patient Health Questionnaire-9 (caregiver subject)
5. FAMCARE-10 (caregiver subject)
6. Resource Use Instrument
7. KATZ ADL (caregiver and patient)
8. KATZ comorbidity questionnaire (caregiver subject)
9. Cohen Mansfield Agitation Inventory
10. Revised scale for caregiving self-efficacy (caregiver subject)
11. Neuropsychiatric Inventory Questionnaire

**Description of Instruments Created By Research Team**

1. Patient demographics
2. Caregiver demographics
3. Record of advance care planning documentation and preferences for care
4. Financial burden questionnaire

**Audio / Photo / Video Recording** No**Deception** No**Results of the Study Will Be Shared** Yes  
with Subjects or Others**How the Results Will Be Shared**

1. Peer review publication
2. Presentation at conferences

**When the Results Will Be Shared**

After the conclusion of the study and completion of analysis

**15. Procedures - Instruments****Instruments Created By Research Team**

**Type** Study team created instruments  
**Name**  
**Upload** Study instruments.docx

**16. Procedures - Compensation**

Compensation for Participation      No

## **17. Consent - Obtaining Consent**

**Consent Process**

Adult Consent, Legally Authorized Representative (LAR) Permission

**Where and When Consent Will Be Obtained**

Consent will be obtained at enrollment. Consent forms will be emailed to the patient or their proxy and the caregiver subject. The RC will ensure that the subject has understood all elements of the consent form and had adequate time to read them prior to enrollment.

**Waiting Period for Obtaining Consent**

Patients and caregiver will be given a study information leaflet prior to the study team obtaining consent. This will be emailed to the patient or their legally authorized representative and their caregiver.

In all cases, the study team will ensure the LAR has had sufficient time to read the study information, ask any questions, and will provide the possibility of contacting the study team at a later date if they require further time to consider participation.

**SOP HRP-090 Informed Consent** Yes

**Process for Research Is Being  
Used**

**PPHS Worksheets, Checklists and SOPs**

**Process to Document Consent in  
Writing** Will Use Standard Template

**Non-English Speaking Participants  
Will Be Enrolled** Yes

**What Languages Other Than English Will Be Used**

Spanish

**What Process Will Be Used** Long Form

***The consent document must be translated into the language of the potential subject, and approved by the IRB, before you can go through the consent process with the non-English speaking person. If, after the project is approved, a short form consent process is needed, please see the PPHS policy and submit a modification.***

## **18. Consent - Legally Authorized Representative**

### **Process to Determine Whether an Individual is Capable of Consent**

Capacity to consent will be determined by a qualified attending physician with the necessary license, training, and certification who is familiar with the patient's clinical situation (in most cases, this will be the physician who provides authorization for the study team to introduce the study to the dyad).

The capacity assessment will focus on the subject's understanding of the purpose of the study, the experimental nature, risks and intended benefits, the right to withdraw, and alternatives to participation. The assessment of capacity will include a determination of the cause and extent of the incapacity and the likelihood that the subject will regain capacity. The determination of capacity procedure and results will be documented in the electronic medical record, and a copy kept for the research study.

For patients lacking capacity to consent to participation (likely the majority) we will require consent from the patient's legally authorized representative (LAR).

In the unlikely event that the patient has capacity to consent to participation at baseline, it is likely that they will subsequently lose capacity to consent during the study period. Therefore, even where patients have capacity, as an additional safeguard we will seek additionally seek the consent of the LAR at baseline, such that if the patient subsequently loses capacity, we can transition to LAR consent.

We have understood and will follow the procedures outlined in the following policies and documents: A3-113 and A3-113.9 and HRP-422.

### **Prioritized List of Individuals from whom Permission will be Obtained**

In accordance with SOP HRP013, we will define the prioritized list of individuals who can act as the patient's legally authorized representative as a court appointed guardian who is specifically given authorization to consent to participation in research. In the absence of a court appointed guardian who is specifically given authorization to consent to participation in research, any of the following individuals:

1. A court appointed guardian who is specifically given authorization to consent to health care
2. A previously designated health care proxy
3. Spouse (if not legally separated) or domestic partner
4. Children > 18 years of age
5. Parents
6. Siblings > 18 years of age

This is in accordance with New York State Law (New York Family Health Care Decisions Act, Mental Hygiene Law) and Mount Sinai Policies.

### **Process for Assent of the Subjects**

Where patients lack capacity to consent, we will seek assent to study participation where they are capable of being consulted.

We will seek patient assent for all procedures/ interactions with the clinical team members (as would happen in the normal course of clinical care) where capable of being consulted. Dissent will always be respected.

***For research conducted in New York State, review “SOP HRP-013 Legally Authorized Representatives, Children, and Guardians” to be aware of which individuals in the state meet the DHHS and FDA definition of “legally authorized representative.”***

***For research conducted outside of New York State, obtain consultation from Mount Sinai legal counsel as to the definition of “legally authorized representative” in the jurisdiction(s) where you are performing your research. After receiving consultation with Legal, provide an explanation in this section about which individuals are authorized under applicable law to consent on behalf of a prospective subject to their participation in the procedure(s) involved in this Human Research.***

**19. Consent - Documents****Consent Documents**

Type	Patient without capacity
Name	
Upload	Adult without capacity 5.22 COVID_clean.docx
Type	Patient with capacity
Name	
Upload	Adult with capacity COVID amended - clean 5.22.docx
Type	Caregiver
Name	
Upload	Caregiver consent clean 5.22 for COVID.docx

***Consent Templates***

## **20. Data - Collection**

**Health Related Information Will Be Yes  
Viewed, Recorded, or Generated**

**Description of Health Information That Will Be Viewed, Recorded, or Generated**

Data warehouse query (screening purposes):

1. Patient name
2. Patient MRN
3. All encounters within the Mount Sinai system in quarter of request and 12 months prior:
  - a. Encounter ID
  - b. Dates of encounter (admit and discharge)
  - c. Encounter type (e.g., outpatient, inpatient)
  - d. Discharge disposition
  - e. Discharge location to
  - f. ICD10 code and diagnosis description
  - g. ICU admission
  - h. Encounter site
  - i. Provider
  - j. Payer
  - k. Wheelchair order
  - l. Hospital bed order
4. Patient zipcode
5. Patient date of birth

From this information, we will generate a list of patients with a diagnosis of dementia. We will then review the charts of these patients to determine potential eligibility.

Chart review (screening purposes):

1. Name, MRN, date of birth
2. Physician note of behavioral or psychological symptoms of dementia (yes/no)
3. Psychotropic medication (yes/no; type)
4. Documented MMSE < 20 in past 6 months (yes/no).
5. Evidence of any of the following: needs assistance with dressing, bathing, toileting; urinary or fecal incontinence; weight loss; dysphagia/ aspiration; immobility; loss of ability to communicate (yes/no; checkbox for each)

Interviews (enrolled subjects):

Patients:

Demographics (study team)  
Symptoms (SM-EOLD) - standardized  
Quality of life (QOL-AD) - standardized  
Function (KATZ ADL and IADL) - standardized  
Resource use (RUI) - standardized  
Care preferences - study team  
Cohen Mansfield Agitation Inventory - standardized  
Financial burden - study team  
Neuropsychiatric Inventory Questionnaire - standardized

Caregivers:

Caregiver demographics (study team)  
Caregiver burden (Zarit Burden Inventory) - standardized  
Caregiver depression (PHQ-9) - standardized  
Caregiver satisfaction with care (FAMCARE-10) - standardized  
Caregiver self efficacy (revised scale for caregiving self-efficacy) - standardized  
Caregiver comorbidities (KATZ) - standardized

Chart reviews at baseline and follow up (enrolled subjects)

1. Medications (name, dose)
2. Hospitalizations and ED visits in past 12 months (yes/ no/ number)
3. Advance care planning documentation
4. Receipt of any of the following: (i) IV fluids (ii) IV antibiotics (iii) PEG (iv) Intubation (v) CPR

Data warehouse (enrolled subjects):

All encounters in the Sinai health system from enrollment until study termination:

1. Patient name
2. Patient MRN
3. All encounters within the Mount Sinai system in quarter of request and 12 months prior:
  - a. Encounter ID
  - b. Dates of encounter (admit and discharge)
  - c. Encounter type (e.g., outpatient, inpatient)
  - d. Discharge disposition
  - e. Discharge location to
  - f. ICD10 code and diagnosis description
  - g. ICU admission
  - h. Encounter site
  - i. Provider
  - j. Payer
  - k. Wheelchair order
  - l. Hospital bed order
4. Patient zipcode
5. Patient date of birth
6. Costs associated with care

**Non-Health Related Information Will Yes  
Be Viewed or Recorded**

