#### **Objectives**

The objective of this study is to determine whether a new home based palliative care program for patients with advanced dementia: 1) Improves overall symptom control and quality of life in patients with dementia; 2) Reduces caregiver burden, increases caregiver satisfaction, reduces caregiver depression; and 3) Reduces healthcare utilization (number of hospital admissions, days in hospital, emergency department visits) and increases days at home.

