#### **Primary and Secondary Study Endpoints**

1. Patient symptoms and quality of life (co-primary endpoints). Measured using Symptom Management at the End-of-Life in Dementia (SM-EOLD) and Quality of Life in Alzheimer's Disease (QOL-AD) respectively. Measured at baseline, 3 months, 6 months.
2. Caregiver burden, satisfaction with care, and depression. Measured using Zarit Burden Inventory, FAMCARE-10, and Patient Health Questionnaire 9 (PHQ-9) respectively. Measured at baseline, 3 months, 6 months. We will also study the effect of the intervention on caregiver self-efficacy, using the revised scale for caregiving self-efficacy.
3. Healthcare utilization: from the data warehouse as well as using the Resource Use Instrument (RUI) collected through interviews with patients. Healthcare cost: measured through the Mount Sinai Data Warehouse.

Study duration is 6 months.

**Protocol Was Already Approved** No  
by the Icahn School of Medicine at  
Mount Sinai (ISMMS) Institutional  
Review Board (IRB) Under a  
Different Principal Investigator

**Protocol Was Previously Submitted** No  
to an External(non-ISMMS) IRB

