### **Estimated Date for the Investigators Within 3-5 years to Complete This Study**

### **Procedures for Subjects to Request Withdrawal**

At the time of enrollment, we will emphasize subjects' right to withdraw. If a subject/ their LAR wishes to withdraw, they will make contact with either the research staff or the Principal Investigator. When this happens, the research coordinator will complete a study termination form to indicate subject withdrawal from the study. We will record why the subject wished to withdraw (with their or LAR agreement) as this will provide additional data around the acceptability of the intervention. Where subjects/ LAR wish to withdraw from the study, we will request permission to collect information from their routine medical care (for patients only), as documented on the consent form.

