### **Procedures for Investigator to Withdraw Subjects**

1. Death of patient (caregiver will be withdrawn)
2. No available caregiver
3. Transition to long term care (patients and caregivers)
4. Transition to skilled nursing facility for longer than 30 days (patients and caregivers)
5. Inpatient hospitalization for longer than 30 days (patients and caregivers)
6. Relocation of patient outside of Manhattan
7. Safety of clinical team cannot be assured
8. Study stopped
9. Principal Investigator deems it to be in the subject's best interest
10. The subject withdraws permission to use their PHI for research

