### **Anticipated Circumstances of Subject Withdrawal**

While we do not anticipate subjects wishing to withdraw, we do have procedures in place should subjects wish to withdraw and these are detailed in the consent form and will be emphasized by the research coordinator at the time of enrollment. Subjects will be withdrawn if they die, they transition to long term care, they have a hospital stay exceeding 30 days, or they relocate outside of Manhattan.

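### Utilization has two inconsistent collection windows, neither stated as six months from randomization for every patient, so follow-up may end at exits related to the outcome

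*Protocol*

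**What the plan says.** Among the aims in Protocol section 3 (Objectives) is that the program "Reduces healthcare utilization (number of hospital admissions, days in hospital, emergency department visits) and increases days at home". The endpoints paragraph of that section adds: "Study duration is 6 months".

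Section 20 describes the warehouse extract for enrolled patients as "All encounters in the Sinai health system from enrollment until study termination". Item 3 of the same list reads "All encounters within the Mount Sinai system in quarter of request and 12 months prior", which repeats the item used for the screening query.

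Section 9 governs exits. When a subject or representative asks to withdraw, "the research coordinator will complete a study termination form to indicate subject withdrawal from the study", and permission is sought to go on collecting the patient's routine-care information. A separate list covers withdrawal by the investigator. It includes an inpatient or skilled nursing stay of more than 30 days, entry to long-term care, and having no available caregiver. It says nothing about further data collection. Section 24 repeats part of that list: subjects are withdrawn if "they have a hospital stay exceeding 30 days, or they relocate outside of Manhattan".

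Section 12 also requests warehouse and claims data on utilization, without dates. SAP section 4 plans simple counts of admissions, hospital days, days out of hospital and ED use, then descriptive statistics by group. It mentions no window, follow-up time, withdrawal or death.

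**The concern.** Counts compare two arms fairly only if every patient is observed for the same period, or if the analysis allows for the difference. Here the period is not fixed, and several exit rules are themselves heavy use of care or closely tied to it. If the extract ends at exit, a patient with a very long stay contributes no later encounters, and perhaps not the rest of that stay.

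Long stays are part of what the program hopes to prevent. If usual-care patients have more of them, truncation would hide some of the benefit. But entry to long-term care or loss of a caregiver would also stop the count, and an arm with more such exits would appear to use less hospital care. The direction of any bias cannot be predicted. Days out of hospital, and with them days at home, are the most exposed, because they depend directly on how long the patient is observed. An undefined window could also end up being chosen after results are visible.

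**Working it through.** The documents give no rate, variance or power figure for utilization, and the Protocol refers the power analysis to a separate proposal. There is therefore no figure of the plan's own to reproduce. The check follows each reading of the window, then illustrates the size on stated assumptions.

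**Reading 1: termination is the individual's exit.** A completer is observed for about six months, as intended, so the gap lies with early exits. Take a hypothetical patient admitted on day 20 for 45 days, with 182 days of intended follow-up and no later stay.

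- Withdrawal falls at about 20 + 30 = day 50. Unobserved time is (182 − 50)/182 = 132/182 = 73%.
- If the stay is counted only to withdrawal, about 30 of its 45 days are counted. If it is counted from its admission and discharge dates, all 45 are, and unobserved time starts at discharge on day 65: (182 − 65)/182 = 117/182 = 64%.
- Days out of hospital over the full period are 182 − 45 = 137. Computed from time observed to day 50, they are 50 − 30 = 20.

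**Reading 2: termination is the end of the whole study.** Assume uniform entry over the two years stated in section 9 and closure six months after the last entry, at month 30. Observation runs from 30 − 24 = 6 to 30 − 0 = 30 months, with mean (6 + 30)/2 = 18. Only 6/18 = 33% of person-time lies in the program period. Everyone's six months are captured, but a plain count over the extract mixes patients whose exposure differs up to fivefold (30/6). Randomization balances entry dates on average, so the harm here is mainly noise and dilution.

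**Reading 3: quarter of request plus 12 months.** Assume a single request at month 30; the Protocol does not say how many requests are made. The window reaches back 12 to 15 months, to month 18 or 15. The full six months are captured only for patients who entered after that: (24 − 18)/24 = 25%, or (24 − 15)/24 = 37.5%. Repeated requests would close this gap.

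**Size under reading 1.** A simulation used 40,000 patients per scenario over 180 days. None of its assumptions come from the documents: Poisson admissions at 0.5, 1.0 or 1.5 per 180 days; lognormal stays with a median of 6 days; 1%, 3%, 5% or 10% of stays over 30 days; and counting stopped at day 30 of the first such stay. At 1.0 admission per 180 days:

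| Stays over 30 days | Mean hospital days, full / cut | Mean admissions, full / cut |
|---|---|---|
| 1% | 7.10 / 7.00 | 0.961 / 0.957 |
| 3% | 7.83 / 7.47 | 0.950 / 0.943 |
| 5% | 8.58 / 7.87 | 0.951 / 0.939 |
| 10% | 10.68 / 8.57 | 0.943 / 0.923 |

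Across all twelve scenarios, hospital days are understated by 1.1% to 19.9% and admissions by 0.1% to 3.3%, with 0.4% to 11.1% of patients withdrawn by the rule. Most of the loss in days comes from cutting the triggering stay. If that stay is counted in full, only later stays are lost. Stay lengths are drawn independently, so the share of days lost is then close to the share of admissions lost, about 3% at most.

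**Difference between arms, triggering stay cut at day 30.** Suppose the arms differ only in the share of stays over 30 days, at 1.0 admission per 180 days.

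- 5% against 3%: a true difference of 0.67 days becomes 0.33 (about 50%).
- 5% against 2%: 1.09 becomes 0.55 (about 50%).
- 10% against 5%: 2.04 becomes 0.59 (29%).

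These ratios carry simulation error. The table's separate runs give (7.87 − 7.47)/(8.58 − 7.83) = 0.40/0.75 = 53% for 5% against 3%, and (8.57 − 7.87)/(10.68 − 8.58) = 0.70/2.10 = 33% for 10% against 5%. The simulation leaves out ED visits, deaths, the other exit rules and differences between patients in admission rate, so it is not a bound.

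**The case against.** A reader might infer that the extract certainly stops at a patient's own exit, so that hospital days, admissions and ED visits are all cut off by their own values. The documents do not support that.

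- The term is never defined. Its only link to an individual is the form named under withdrawal at the subject's request. The investigator's list, which holds the 30-day rule, does not use the term.
- The extract includes admission and discharge dates. A stay that begins inside the window may be counted in full, and nothing says it is clipped.
- The trigger is one long stay, not total days. Three stays of 25 days make 75 hospital days and trigger nothing. Admissions and ED visits can be cut only by a related event.
- Under the whole-study reading, dated encounters can be restricted to six months at analysis. The second window may be text carried over from the screening query.
- Claims data, and chart abstraction after each hospitalization, could fill gaps. The consent form and the accompanying proposal, which are not among the documents reviewed, may settle part of this.
- Utilization is not co-primary, SAP section 4 is descriptive, and section 24 calls the trial a pilot.

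These points limit what can be claimed and how serious it is. They do not supply a window. The claims request has no dates. The chart review looks back 12 months, so at month 6 it reaches 12 − 6 = 6 months before enrollment. No text provides for data after withdrawal by the investigator, and no text restricts the counts to six months.

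**Conclusion.** The concern holds in this form: the Protocol gives two inconsistent windows for enrolled patients' utilization, neither is stated as six months from randomization for every randomized patient, and SAP section 4 does not repair this. Under the individual-exit reading, which the wording of the withdrawal form suggests but does not establish, follow-up ends at events related to the outcome. Later encounters are lost, and possibly the rest of the triggering stay. Under the whole-study reading, exposure is unequal. Under the request-based reading, part of the six months may be missed.

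The size cannot be derived from the documents. The 1.1% to 19.9% understatement of hospital days rests on assumed rates and on clipping the triggering stay. Without clipping, the same assumptions give about 3% at most. The 25% to 37.5% coverage figure rests on a single late request.

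This should be fixed before the arms are compared. It does not bear on the co-primary endpoints.

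**What to change.** In Protocol section 20, replace both windows with one: every warehouse and claims encounter from randomization to six months, or to death if earlier, for every randomized patient. Count all in-window days of any stay. Keep the 12 months before randomization as a separate baseline extract.

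In section 9, define study termination and state that withdrawal by the investigator does not end this passive extract. Two limits stay in force: withdrawn permission to use health information ends it, and the existing request for permission applies when the subject or representative asks to withdraw.

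In SAP section 4, count over that fixed window and state how follow-up shortened by death or refused permission is handled, for example by reporting observed time by arm and rates alongside counts.

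The cost is wording in three places, a revised data request, and IRB confirmation that existing authorization covers the extract after withdrawal by the investigator. No patient contact is added, and the withdrawal rules themselves need not change. It should be done before identifiers are removed, since the extract depends on them.
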